### Specific Aim 1: To quantify the short-term effect of T in infants with XXY on cardiometabolic outcomes.

**Hypothesis:** Percent body fat (%BF) will follow a normal trajectory in treated infants, while infants not receiving T will have greater %BF. **Approach:** In the TESTO: Testosterone Effects on Short-Term Outcomes trial, infants with XXY (n=75) age 4-12 weeks will be randomized 1:1 to receive 25mg intramuscular T injections every 4 weeks for 3 doses or placebo. %BF will be assessed by air displacement plethysmography at baseline, 12 weeks, and 24 weeks. The primary outcome is change in %BF z-scores at 12 weeks between groups (powered to detect a difference of 0.5SD). Infants initially receiving placebo will get T in the second half of the study (12-24 weeks). Secondary outcomes include change %BF z-scores from 12-24 weeks, growth parameters, and serum leptin.

**Specific Aim 2: To quantify the short-term effects of T in infants with XXY on neurodevelopment, gonadal function and safety outcomes.**

**Hypothesis:** (1): XXY infants receiving T will have greater gains in standard scores on early motor skills, emerging language, and adaptive functioning. (2): T treatment will not impair gonadal function, as measured by gonadotropins and biomarkers of Sertoli cell function. (3): There will be no serious adverse outcomes associated with T treatment in infants with XXY. **Approach:** Infants from Aim 1 will be given standardized neurodevelopment assessments at baseline, 12 and 24 weeks. Serum hormone biomarkers of gonadal function will also be obtained at these times. Adverse events will be monitored throughout the study.

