## II. Background and Significance:

**XXY/Klinefelter syndrome is common and the diagnosis in childhood is increasing.** An extra X chromosome is present in ~1/600 boys, therefore over 6 million boys and men worldwide are affected by this very common, but under-diagnosed, genetic condition known as XXY or Klinefelter syndrome (KS). XXY is characterized by a high degree of phenotypic heterogeneity throughout the lifespan but nearly universal testicular insufficiency and infertility in adulthood. Our knowledge of the natural history of XXY in infancy and childhood is largely limited to birth cohort studies from the 1970's and more recent cross-sectional studies limited by ascertainment bias. Historically, less than 10% of males with XXY are diagnosed before adolescence, however the rate of prenatal diagnosis is increasing exponentially as testing of free-fetal DNA in maternal blood evolves to become standard screening in prenatal care. Furthermore, there is evidence the actual incidence of XXY is increasing as well. With greater recognition in infancy and potentially increased prevalence of XXY, there is a high demand for evidence-based research, particularly investigation of early determinants that contribute to increased morbidity and decreased quality of life in this population.

**XXY results in universal testicular dysfunction and hypogonadism.** While many features of the XXY phenotype are variable, testicular dysfunction is nearly universal. In adults, this manifests as small testes, infertility, and hypergonadotropic hypogonadism (elevated gonadotropins and low testicular hormone concentrations). The Leydig cells in the testes produce testosterone (T) and insulin-like hormone 3 (INSL3), while the Sertoli cells produce inhibin B (INHB) and anti-mullerian hormone (AMH). All of these testicular hormones have been demonstrated to be lower in XXY when compared to typical males from mid-puberty through adulthood. Microscopically, the testes of men with XXY are fibrotic with rare germ cells and Leydig cell hypertrophy.

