**3. VENIPUNCTURE.** Venous blood samples will be drawn in the morning a minimum of 180 minutes after eating (fasting for an infant.) The collection of blood samples may result in temporary discomfort, bruising, bleeding, and on rare occasions, infection. Standard hospital precautions for venipuncture will be followed. Anemia is also a risk; the routine guidelines in our Pediatric CTSC are 2.5 ml/kg per blood draw. We will draw 8 ml of blood per visit. If the subject is <3.2kg on the first visit we will reduce the amount of blood to be drawn.

*Likelihood of experiencing any risk: moderate (temporary discomfort).*

*Likelihood of experiencing serious risk: very low*

**Hormones.** Serum will be processed and stored at -80 degrees until batch analysis for quantification of LH, FSH, total and free T by liquid chromatography tandem mass spectroscopy (LC/MS), AMH, INHB, estradiol and leptin. Serum testosterone, inhibin B, AMH, estradiol and gonadotropins at baseline will allow us to assess endogenous testicular function. Hormone concentrations after testosterone exposure will serve as a short-term safety measure of testicular function. Exploratory aims may include looking at whether baseline serum testosterone predicts change in our outcomes after testosterone exposure. Leptin is biomarker of adiposity and will be used as a secondary measure to support our Peapod findings. Our previous work has shown that leptin concentrations are higher in boys with Klinefelter syndrome and this study will be the first to assess this in infants and explore how testosterone supplementation alters leptin in this population. Finally, we will measure serum lipids (triglycerides and HDL) and insulin as markers of insulin resistance using Trig/HDL ratio and 1/insulin as estimates. There are very limited validated assessments of cardiometabolic health in infants, therefore these data will largely be exploratory. If blood volume is limited, the order of priority for serum measurements will be as follows: Testosterone > inhibin B > leptin > gonadotropins > AMH > lipids > insulin > estradiol. Additional serum may be saved for future analyses.

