For **specific aim 3 (exploratory)**, we will compare C14:1 concentrations (an easily identified LCAC) between treatment groups at 12 weeks using two-sided t-tests, hypothesizing C14:1 will be lower in the T treated group (representing improvement in fatty acid oxidation and energy metabolism). This aim is exploratory; with 10 subjects per group we will have 80% power to detect a difference of 1.3 SD with a two-sided alpha of 0.05. Then, paired t-tests will be used to compare C14:1 before and after T treatment (5 paired samples), with similar power. We will analyze secondary outcomes including other LCAC and BCAA (leucine, isoleucine, and valine) in a similar fashion. Next, we will use principle component analysis on the entire dataset from the comprehensive untargeted analysis to identify patterns and pathways altered with T treatment. The spectra data file from the non-targeted metabolomics panel will be uploaded to MetaboAnalyst, and the software will be used for Metabolite Set Enrichment Analysis as well as Pathway Enrichment Analysis. We will have >80% power to detect at least 2-fold changes between T treated and untreated using a significance level of 0.0001 (less than two false positives based on the conservative Bonferroni correction for multiple comparisons). We will also input the analytes into known KEGG pathways of energy metabolism to look for pathway enrichment.

Table 2. Summary of primary and secondary outcome measures for each Specific Aim (SA).

SA	Primary Outcome	Weeks		Measurement Tool
		12	24	
SA 1: Cardiometabolic	Change %BF z-scores from baseline	X		PeaPod
	Secondary Outcomes			
	Change %BF z-scores from baseline		X	PeaPod
	Change in height, weight, weight-for-length and waist circumference z-scores from baseline	X	X	Physical exam measurements
	Serum leptin, lipids, and insulin	X	X	Immunoassays in CCTSI core laboratory
SA 2	Primary Outcome			

	Change in motor composite from baseline	X		AIMS percentile composite score (all domains)
	Secondary Outcomes			
	Serum LH, FSH, INHB, AMH, E2 and Total T	X	X	Immunoassay and LC/MS ([name] lab)
	Change in gross and fine motor scaled scores	X	X	Scaled scores on all PDMS-2 domains, AIMS
	Cognitive and Language composite scores	X	X	Bayley III: cognitive and language domains
	Adaptive functioning	X	X	ABAS III standard scores
	Number of adverse events	X	X	Verbal questionnaire, parent-report
SA 3: Metabo- Iomics	Primary Outcomes			

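### On-treatment testosterone, estradiol, LH and FSH are used as safety measures of testicular function, but in treated infants they are ambiguous and cannot support a conclusion of no gonadal impairment.

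*Combined protocol and SAP*

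**What the plan says.** All references are to the combined protocol and SAP.

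- Section IV.D.3 (Venipuncture, Hormones) lists the panel: "quantification of LH, FSH, total and free T by liquid chromatography tandem mass spectroscopy (LC/MS), AMH, INHB, estradiol and leptin". It ties the baseline sample to the infant's own function: "Serum testosterone, inhibin B, AMH, estradiol and gonadotropins at baseline will allow us to assess endogenous testicular function". The next sentence extends this to treated infants: "Hormone concentrations after testosterone exposure will serve as a short-term safety measure of testicular function". No hormone is set aside for the post-dose samples.
- Table 2 (section IV.F) has one Aim 2 secondary-outcome row, "Serum LH, FSH, INHB, AMH, E2 and Total T", marked for weeks 12 and 24.
- Section I, Specific Aim 2, hypothesis (2): "T treatment will not impair gonadal function, as measured by gonadotropins and biomarkers of Sertoli cell function".
- Section IV.F compares gonadal function between T and placebo descriptively. It gives no margin and no rule for reading any single marker.
- Section IV.D.3 sets the assay order when serum is short: "Testosterone > inhibin B > leptin > gonadotropins > AMH > lipids > insulin > estradiol". The order is the same at every visit.
- Section IV.C has the DSMB review testicular function without preset criteria.

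**The concern.** A marker of testicular function should respond to what the testes do. Once an infant has been injected with T, serum T and the estradiol formed from it no longer do only that. LC/MS gives a concentration, and nothing in the plan separates injected from testicular T. LH and FSH are under feedback from circulating T, so a rise that would otherwise point to a failing testis can be masked. These links are general endocrinology and are not spelled out in the plan.

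The problem reaches the hypothesis itself, because hypothesis (2) names gonadotropins. Section IV.G makes the absence of safety issues one of the conditions for supporting this therapy. A descriptive table showing comparable or higher T and unremarkable LH and FSH in treated infants could be cited as reassurance that it cannot give.

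**Working it through.** The plan states no sample size, margin or power for gonadal function, so there is no figure of its own to reproduce. The check has three steps.

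**1. Days from last T dose to blood draw.** Inputs from section IV.C: injections at weeks 0, 4, 8, 12, 16 and 20, the first three T in one arm and the last three T in the other. Visits are at week 12 ± 10 days and week 24 ± 10 days. Injections are taken as given on schedule.

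- T-first arm, Visit 2: 84 − 56 = 28 days; with the window, 18 to 38.
- T-second arm, Visit 3: 168 − 140 = 28 days; with the window, 18 to 38.
- T-first arm, Visit 3: 168 − 56 = 112 days; with the window, 102 to 122.

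**2. How much drug could remain.** The documents give no half-life, so a range of 4 to 21 days is assumed. With three equal doses 28 days apart and first-order decay, the residue as a share of one dose, t days after the last, is

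r(t) = 0.5^(t/h) + 0.5^((t+28)/h) + 0.5^((t+56)/h).

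Example with h = 8 and t = 28: 0.0884 + 0.0078 + 0.0007 = 0.0969, or 9.7%.

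| Assumed half-life (days) | Day 18 | Day 28 | Day 38 | T-first arm at week 24 (days 102 to 122) |
|---|---|---|---|---|
| 4 | 4.5% | 0.8% | 0.1% | 0.0% |
| 8 | 23.0% | 9.7% | 4.1% | 0.016% to 0.003% |
| 12 | 43.8% | 24.6% | 13.8% | 0.34% to 0.11% |
| 16 | 63.5% | 41.2% | 26.7% | 1.7% to 0.7% |
| 21 | 85.8% | 61.7% | 44.3% | 5.4% to 2.8% |

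On treatment the residue could be anywhere from 0.1% to 85.8% of a 25 mg dose. In the T-first arm at week 24 it is at most 5.4%. These are drug amounts, not serum concentrations, and the documents give no endogenous level to set them against. The drug's share of measured T therefore cannot be computed.

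**3. What each Table 2 hormone can show in an infant recently given T.**

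- Total T (free T is also assayed): drug plus testicular output, in unknown proportion.
- Estradiol: formed partly from that same mixture.
- LH and FSH: subject to feedback. A low value may be drug suppression of the axis. A normal value may be a raised one pulled down.
- Inhibin B and AMH: Sertoli-cell products according to section II, and not the injected substance. They may still shift indirectly if FSH is suppressed.

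Four of the six hormones are thus exposed to the drug or its feedback, and two are less confounded. At week 24 the comparison is weaker still, because both arms have had T by then and section IV.E concedes that the second half has no control group.

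**The case against.** A reader might infer that the treated arm will look unimpaired whatever happens to the testes. The documents do not support that:

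- Inhibin B and AMH are in the same panel and the same Table 2 row. Testicular size is examined at all three visits (sections IV.C and IV.D.5). The hormones are listed separately, not combined into a composite.
- Hypothesis (2) does not name T or estradiol. Of the four affected markers it relies only on LH and FSH.
- The signature "hypergonadotropic hypogonadism (elevated gonadotropins and low testicular hormone concentrations" in section II describes adults, so it does not establish that a fall in LH and FSH would be read as healthy in an infant. For boys aged 4 to 12, section III takes low inhibin B as the evidence of testicular failure.
- Section I treats activation of the axis in early infancy as normal. Suppressed LH and FSH could therefore be read as harm. The markers are ambiguous, not always falsely reassuring.

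A reader might also infer that treated infants' total T mainly reflects the days since injection. That depends on a half-life the plan does not give; at the short end of the assumed range little drug is left.

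The T-first arm's week-24 sample is largely off drug, so its hormones should not be discarded. Dropping LH and FSH from safety reporting would lose evidence of axis suppression. The assay order is a minor matter: inhibin B is already second, leptin is an Aim 1 secondary outcome, and post-dose T is a useful exposure check when parents inject at home.

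All of this stands and narrows the point. None of it supplies a rule for reading on-treatment T, estradiol, LH and FSH, and the sentence in section IV.D.3 uses them without qualification.

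**Conclusion.** The concern holds in a limited form. In samples taken 18 to 38 days after a T injection, the T-versus-placebo contrast in four of the six Table 2 hormones cannot be read as testicular function and cannot support hypothesis (2). The inhibin B and AMH comparison is not undone, and no particular direction of bias is shown.

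The amount of contamination is unknown and could be negligible or large; the 0.1% to 85.8% range rests on assumed half-lives and on-schedule dosing. The week-12 comparison also assumes that the blood draw precedes the week-12 injection, which the plan does not state. Without that order, a T-second infant seen late in the window could already have received T.

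This is a secondary outcome analysed descriptively, so the consequence lies in the wording of the safety conclusion. The correction is cheap and makes that conclusion more defensible.

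**What to change.** Amend hypothesis (2) in section I, section IV.D.3, section IV.F and Table 2 as follows.

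- (a) At on-treatment visits (T-first arm at Visit 2, T-second arm at Visit 3), report total and free T and estradiol as exposure measures, with days since last injection, and not as testicular-function safety measures. Injection dates can come from the administration log and the post-injection survey.
- (b) Keep LH and FSH in safety reporting as measures of axis suppression. State that low or normal on-treatment values are not evidence of unimpaired testes.
- (c) Base the hypothesis (2) conclusion mainly on the randomised week-12 comparison of inhibin B and AMH, noting that both may shift indirectly if FSH is suppressed.
- (d) Report the T-first arm's week-24 hormones as a largely off-drug check, stating that there is no untreated comparator.

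Optionally, since AMH becomes one of the two main markers, consider moving it up the low-volume assay order at Visits 2 and 3. That is a trade-off against the markers it would overtake.

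Items (a) to (d) need only wording, with no extra blood or visits. The downside is that the gonadal-safety conclusion rests on fewer markers.

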#### **E. Potential Scientific Problems:**

Recruitment and retention of subjects with rarer pediatric conditions can be problematic, however with our successful feasibility study and accommodation for participant travel in this budget, we do not anticipate enrollment as an obstacle. Utilizing a cross-over-type design reduces our major parental reservation of the study, which is the possibility of being randomized to not receive T, and still allows us to evaluate short-term effects of T and observe the metabolic pathways that have been altered. As with all clinical research, we acknowledge there will be ascertainment bias and strict inclusion criteria that may limit the generalizability of our results. Our proposal only includes prenatally diagnosed infants, however our previous work demonstrated no differences in cardiometabolic or gonadal function between pre- or postnatally diagnosed XXY boys therefore results from these outcomes should be generalizable. Finally, to further assess the external validity of our study we will collect and compare basic demographic data from families who decline study participation, and will also compare our study cohort to our historic data of infants who are seen in our eXtraordinary Kids Clinic.

Results and interpretation from the second half of the participant protocol (weeks 12-24) does require certain assumptions, including that this larger study finds similar differences in body composition between treated and untreated infants as our pilot study did. There will not be a control group as part of this study for the second half of the study, but importantly these outcomes are all secondary. In addition, we are concurrently recruiting for a natural history study in infants with X&Y chromosome variations (eXtraordinary Babies) that includes 100 infants with XXY who will have body composition assessments (PeaPod and later DEXA). Some of these will be infants participating in this study, but presumably an important subset will not be in the TESTO study and will not have received testosterone clinically. Finally, data from the Health Start Study of healthy local infants can serve as a non-XXY control group for normal adipose accumulation in infancy.

Our study does not address the large phenotypic variability in XXY. It is possible we will fail to find a difference in outcomes with T treatment because some boys with XXY have adequate gonadal function or have polymorphisms in their androgen receptor gene. If we fail to find a difference in our primary outcomes, we will perform post-hoc sub-analyses controlling for age and baseline testosterone concentrations. In addition, DNA will be extracted and saved for future genomic analysis, including sequencing of the androgen receptor gene and other polymorphisms that have been associated with phenotypic variability in XXY.

Finally, we acknowledge there are many factors that influence body composition. These potential confounders will be minimized due to our randomized design and inclusion/exclusion criteria. We will collect data on variables known to contribute to body composition, including race, maternal BMI, maternal weight gain during pregnancy, presence of gestational diabetes, birth weight and gestational age, infant feeding method, and physical therapy interventions. We anticipate our randomized design will minimize differences in these potential confounding variables, however if significant differences are found we will adjust for them in the analyses.

**F. Data Analysis Plan:**

The primary outcome for **specific aim 1** is the change in %BF z-scores between baseline and 12 weeks between treatment groups. Z-scores will be calculated using published norms for age, and the difference between groups will be assessed with a two-sided t-test using an alpha of 0.05. Allowing for a 10% drop-out rate, a sample size of 27 in each group gives us 80% power to detect a difference down to 0.5 z-score change between groups, and >99% power to detect the change score we observed in our pilot study (1.0 z-score change) assuming a variance of 0.65 per our pilot data. We will next use regression models with treatment group, baseline %BF, age of enrollment and feeding method as explanatory variables to assess absolute %BF at 12 weeks. Secondary analyses will include change in %BF z-scores from 12 to 24 weeks 1) in the group receiving T first (are the effects of T maintained or lost?) and 2) in the group receiving T second (does later T have the same effect?). We will analyze anthropometric measurements and serum biomarkers similarly.

For **specific aim 2**, the change in standard scores on developmental assessments will be analyzed in a similar fashion as in specific aim 1. Based on our pilot data, our sample size will yield 80% power to detect a difference between groups of 23 percentile points on the AIMS composite. Secondary analysis will include the changes in scaled scores for the individual Peabody domains and AIMS subtests, the Bayley composite scores, and the ABAS composite at 12 and 24 weeks. Gonadal function and safety outcomes will be compared between subjects on T and placebo using descriptive statistics.

For **specific aim 3 (exploratory)**, we will compare C14:1 concentrations (an easily identified LCAC) between treatment groups at 12 weeks using two-sided t-tests, hypothesizing C14:1 will be lower in the T treated group (representing improvement in fatty acid oxidation and energy metabolism). This aim is exploratory; with 10 subjects per group we will have 80% power to detect a difference of 1.3 SD with a two-sided alpha of 0.05. Then, paired t-tests will be used to compare C14:1 before and after T treatment (5 paired samples), with similar power. We will analyze secondary outcomes including other LCAC and BCAA (leucine, isoleucine, and valine) in a similar fashion. Next, we will use principle component analysis on the entire dataset from the comprehensive untargeted analysis to identify patterns and pathways altered with T treatment. The spectra data file from the non-targeted metabolomics panel will be uploaded to MetaboAnalyst, and the software will be used for Metabolite Set Enrichment Analysis as well as Pathway Enrichment Analysis. We will have >80% power to detect at least 2-fold changes between T treated and untreated using a significance level of 0.0001 (less than two false positives based on the conservative Bonferroni correction for multiple comparisons). We will also input the analytes into known KEGG pathways of energy metabolism to look for pathway enrichment.

Table 2. Summary of primary and secondary outcome measures for each Specific Aim (SA).

SA	Primary Outcome	Weeks		Measurement Tool
		12	24	
SA 1: Cardiometabolic	Change %BF z-scores from baseline	X		PeaPod
	Secondary Outcomes			
	Change %BF z-scores from baseline		X	PeaPod
	Change in height, weight, weight-for-length and waist circumference z-scores from baseline	X	X	Physical exam measurements
	Serum leptin, lipids, and insulin	X	X	Immunoassays in CCTSI core laboratory
SA 2	Primary Outcome			

	Change in motor composite from baseline	X		AIMS percentile composite score (all domains)
	Secondary Outcomes			
	Serum LH, FSH, INHB, AMH, E2 and Total T	X	X	Immunoassay and LC/MS ([name] lab)
	Change in gross and fine motor scaled scores	X	X	Scaled scores on all PDMS-2 domains, AIMS
	Cognitive and Language composite scores	X	X	Bayley III: cognitive and language domains
	Adaptive functioning	X	X	ABAS III standard scores
	Number of adverse events	X	X	Verbal questionnaire, parent-report
SA 3: Metabo- Iomics	Primary Outcomes			
	Change in C14:1 (LCAC) from baseline	X	X	Targeted metabolomics
	Secondary Outcomes			
	BCAA, other LCAC	X	X	Targeted metabolomics
	Pathway analysis	X		Unbiased metabolomics

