## IV. Research Methods

### A. Outcome Measure(s):

#### Primary for Specific Aim 1

Change in %BF z-scores from baseline to 12 weeks (per PeaPod)

#### Primary for Specific Aim 2

Change in motor composite percentile on the AIMS assessment from baseline to 12 weeks

#### Primary for Specific Aim 3

Change in C14:1 long chain acylcarnitine (LCAC) from baseline

**Secondary outcomes:** Change in %BF z-scores from 12 to 24 weeks; change in anthropometric measurements from baseline to 12 and 24 weeks; change in gross and fine motor scaled scores from the PDMS; cognitive and language scores on the Bayley; adaptive functioning from the ABAS; serum hormones, lipids, BCAA, LCAC, and pathway analysis of untargeted metabolomics; urine metabolites; and number and type of adverse events.

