### B. Description of Population to be Enrolled:

A total of 75 infants with XXY will be enrolled. We will include all races, ethnicities, and languages.

*Inclusion criteria:* Male infants with 47,XXY karyotype identified prenatally who are 4-12 weeks old (31 to 90 days of age). 47,XXY must be from a diagnostic test such as CVS, amniocentesis, or post-natal blood/tissue. Non-invasive prenatal screening results alone will not be accepted.

*Exclusion criteria:*

- 1) >20% mosaicism for a normal cell line
- 2) Gestational age at birth <36 weeks
- 3) Birth weight <2.5thile or >97.5thile for age (small or large for gestational age)
- 4) History of thrombosis in self or a first degree relative
- 5) Exposure to androgen therapy outside the study protocol
- 6) Use of medications known to affect body composition, such as growth hormone or insulin
- 7) Known allergy to the testosterone cypionate solution components including benyl benzoate, benzyl alcohol, or cottonseed oil

Involving children is imperative as boys <18 years of age with XXY are much a different population than adult men with XXY. Men with XXY have been shown to have a high prevalence of type 2 diabetes, metabolic syndrome, fatty liver disease, and psychosocial difficulties. Clearly these processes begin in childhood. The potential to intervene in a preventative fashion, prior to the onset of disease, is more promising and productive than trying to treat pre-existing disease. Infant boys are exposed to endogenous testosterone in the first few months of life known as the “mini-puberty period of infancy.” Animal and human studies suggest this is a critical period for biologic programming, and therefore cannot be replicated at any other point in life. Including children in this study design allows us to investigate testosterone as a targeted intervention at this critical time point with evaluation of early markers of disease and disability. The ultimate goal is to improve the lives of children and adults with this condition.

The age of the infants at enrollment was chosen 1) to allow assessment of testicular function during the expected mini-puberty period of infancy, 2) to assure visits 2 and 3 will be completed before the infant is 10kg, as this is the upper weight limit for the PeaPod (our body composition assessment tool), and 3) feedback from parents.

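### The primary Aim 1 t-test ignores baseline %BF; a fixed baseline-adjusted z-score model is a small improvement and should replace adjustment triggered by significant imbalance

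*Combined protocol and SAP*

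**What the plan says.** Section IV.F (Data Analysis Plan) takes the change in %BF z-score from baseline to 12 weeks as the Aim 1 primary outcome, and "the difference between groups will be assessed with a two-sided t-test using an alpha of 0.05". On sample size it says that "a sample size of 27 in each group gives us 80% power to detect a difference down to 0.5 z-score change between groups".

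The next step in the same section is a regression with treatment group, "baseline %BF, age of enrollment and feeding method as explanatory variables to assess absolute %BF at 12 weeks". Its outcome is raw %BF, not the z-score. Anthropometry, serum biomarkers and the Aim 2 developmental scores are to be analysed in the same way as Aim 1.

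Section IV.E (Potential Scientific Problems) adds two conditional adjustments:

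- Data will be collected on "race, maternal BMI, maternal weight gain during pregnancy, presence of gestational diabetes, birth weight and gestational age, infant feeding method, and physical therapy interventions", and "if significant differences are found we will adjust for them in the analyses". No threshold is given, and the analyses affected are not named.
- "If we fail to find a difference in our primary outcomes, we will perform post-hoc sub-analyses controlling for age and baseline testosterone concentrations".

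**The concern.** The plan accepts that baseline %BF and age are worth adjusting for, but does so only in a second model on a different scale. The test that carries the Aim 1 conclusion does not use them, and no adjusted analysis of the z-score is specified. The t-test on change is unbiased over randomisations, but in any one trial its estimate moves with chance baseline imbalance, which baseline adjustment removes.

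The significance-triggered rule in Section IV.E is a separate weakness. In a randomised trial, significant baseline differences arise by chance. The rule therefore selects covariates on imbalance rather than on how well they predict the outcome, and the final model is unknown until the data are seen. Feeding method and therapies are recorded at every visit (Section IV.C, Study Procedures), and Section IV.E does not restrict them to Visit 1 values. As written, the rule could therefore admit variables measured after randomisation.

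At stake are a few points of power and a clear statement of which model governs.

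**Working it through.** **1. Reproduce the plan's figure.** Inputs from Section IV.F: difference 0.5 z, two-sided alpha 0.05, 80% power, 0.65 from the pilot. Section III gives the pilot change scores with ± 0.65 and ± 0.67.

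- Normal approximation: n = 2 × (1.960 + 0.842)² × 0.65² / 0.5² = 26.5, so 27 per arm (power 80.7%). This matches the plan.
- Noncentral t at 27 per arm: 79.2%.
- Taking 0.65 literally as a variance (SD 0.806) needs 41 per arm and gives 62.5% power at 27. The plan's figures therefore reproduce only with 0.65 as an SD.

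The plan states that "A total of 75 infants with XXY will be enrolled". With 10% dropout, 75 × 0.9 / 2 = 33.75, so 33 per arm is also shown; t-test power there is 86.8%.

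**2. ANCOVA on the z-score.** The baseline-to-12-week correlation r and the visit SDs are not in the documents. With equal visit SDs and the change SD held at 0.65, the residual SD is 0.65 × √((1 + r)/2). Unit SDs at both visits imply r = 1 − 0.65²/2 = 0.79.

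Power at a true difference of 0.5 z, model with arm, baseline z and age. The simulation (100,000 trials, age given no effect on the z-score) includes chance covariate imbalance; the noncentral-t formula ignores it.

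| r | Residual SD | 27/arm: t-test, ANCOVA (simulated) | ANCOVA (formula) | 33/arm: t-test, ANCOVA (simulated) |
|---|---|---|---|---|
| 0.9 | 0.634 | 79.4%, 79.8% | 81.2% | 86.9%, 87.5% |
| 0.79 | 0.615 | 79.1%, 81.8% | 83.4% | 86.8%, 89.2% |
| 0.7 | 0.599 | 79.4%, 84.1% | 85.2% | 86.7%, 90.6% |

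Simulated type I error at r = 0.79, 27 per arm: t-test 5.0%, ANCOVA 5.1%.

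**3. Unfavourable case.** Take SD 0.76 at baseline, 1.0 at 12 weeks and r = 0.76. The slope on baseline is 0.76 × 1.0 / 0.76 = 1, and the residual SD is √(1 − 0.76²) = 0.65, so baseline explains none of the change. Simulated power at 27 per arm goes from 79.4% to 77.8%. The SE goes from 0.176 to 0.180, about 2% wider.

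**4. Sensitivity of the t-test to imbalance.** A chance baseline difference of one standard error at 27 per arm shifts the t-test estimate by (1 − r) × visit SD × √(2/27). With visit SDs of 1.45, 1.00 and 0.84 for the three values of r, this is 0.040, 0.057 and 0.069 z, or 8% to 14% of 0.5.

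**5. The Section IV.E trigger.** The list holds eight variables, counting birth weight and gestational age separately. Feeding method is already in the Section IV.F regression, leaving seven. With independence and an assumed p<0.05 trigger, the chance that at least one enters is 1 − 0.95⁷ = 30%. Several of the seven are probably correlated, which would usually lower this.

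To illustrate this type of rule, adjusting for baseline %BF only when it differed significantly gave 79.1%, 79.6% and 79.5% power for the three values of r (27 per arm), almost none of the gain. Baseline %BF is not on the Section IV.E list, so this illustrates the principle and does not evaluate the rule itself.

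**The case against.** **The plan already contains most of the benefit.** The Section IV.F regression is itself an ANCOVA. Simulated with assumed norm curves and without feeding method, its power at 27 per arm is about 79%, 81–82% and 83–84% for the three values of r, within about one point of the z-score model. This stands: what changes is mainly which analysis carries the conclusion. That regression cannot simply be promoted, however, because its outcome is not the primary outcome.

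**The gain is not guaranteed.** Its size and sign depend on quantities that the documents do not give. This also stands, and the range must be quoted with the recommendation.

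**Disagreement between analyses is no argument for the change.** At the design difference, the t-test and the planned regression fall on opposite sides of 0.05 in about 7–10% of simulated trials. A reader might infer that the change removes this conflict. It does not: the z-score ANCOVA and a t-test kept as a sensitivity analysis disagree in about 6–10%. Section IV.F already makes the t-test the governing analysis.

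**The conditional rule might be thought to inflate type I error.** Nothing in the documents supports that. In the baseline-only illustration, rejection under the null did not exceed 5.0%. The full rule, with no stated threshold, cannot be tested.

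**The age and testosterone analyses are already labelled post hoc.** True; calling them exploratory only makes their status uniform.

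**Conclusion.** The point holds as a small efficiency and prespecification improvement. A reader might infer that the primary analysis is invalid or underpowered. The documents do not support that: under randomisation the t-test on change is valid, and with 0.65 as an SD its power is close to the stated 80%.

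For a model with baseline z-score and age at 27 per arm, the expected change in power is about 0 to +5 points for r from 0.9 to 0.7 with equal visit SDs. If the 12-week SD exceeds the baseline SD so that the slope is near 1, up to about 2 points are lost. Adding feeding method was not simulated.

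The firmer part is the Section IV.E rule. It leaves the model open until the data are seen, and the 30% is an upper-end figure under the stated assumptions. The precision that the rule costs cannot be quantified from the documents.

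**What to change.** - In Section IV.F, make the primary Aim 1 analysis an ANCOVA of the 12-week %BF z-score on randomised arm and baseline %BF z-score, with age at enrolment and Visit 1 feeding method, the other covariates that the section already names. Keep the t-test on change as a sensitivity analysis.
- In Section IV.E, replace the significance-triggered adjustment with this fixed Visit 1 set. Label any other adjustment exploratory, including the one for age and baseline testosterone.
- State whether the same model, with the corresponding baseline value, applies to the Aim 2 AIMS change and to the other outcomes now analysed like Aim 1. Otherwise changing Aim 1 leaves those analyses undefined.
- Say that the power statement was derived for the t-test, and call 0.65 an SD.

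The cost is wording: no new data, visits or infants. The statistical cost is one residual degree of freedom per covariate and, if baseline z-score and age add nothing, an SE about 2% wider at 27 per arm.
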